In this study, lower limb stiffness and gait mechanics will be evaluated in healthy, able-bodied adult participants across three conditions; "NoBrace" where participants are asked to walk normally with no bracing, "Stiff" where participants are asked to walk while wearing a Malleo-Lok with stiff struts, "Compliant" where participants are asked to walk while wearing a Malleo-Lok with compliant struts. Testing will occur in a randomized order. Questionnaires will be used to quantify participants' pain and perceived comfort and smoothness during walking. A motion capture system will be used to evaluate walking biomechanics and overall ankle joint level stiffness, allowing for comparisons between conditions. Small reflective markers will be placed on the participant's skin and lower limb forces, and body motion will be assessed using computerized motion capture cameras and force plates in the floor. Muscle activity data will be collected using non-invasive wireless surface electromyography sensors.

Objectives and Specific Aims:

Aim 1: Determine the effect of Malleo-Lok stiffness on lower limb mechanics during gait.

Hypothesis 1.1: We hypothesize that increasing stiffness of the Malleo-Lok will result in decreased ankle range of motion and increased knee flexion during gait.

Hypothesis 1.2: We hypothesize that increasing Malleo-Lok stiffness will result in an earlier, faster center of pressure progression

Aim 2: Determine the effect of Malleo-Lok stiffness on overall joint level stiffness.

Hypothesis 2.1: We hypothesize that measured stiffness will progressively increase between the NoBrace, Compliant and Stiff conditions.

Aim 3. Determine the within-session reliability of a novel in-vivo weight bearing approach to evaluating AFO

stiffness.

Hypothesis 3.1: We expect the novel approach to demonstrate excellent within-session reliability.

Background and Significance:

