A2) Although AFO stiffness is known to influence overall device function for some design approaches[1] AFO stiffness has only been loosely measured in the clinical setting[1,10] and is often subjectively chosen for each patient based on certified prosthetist orthotist (CPO) knowledge and prior experience. Multiple research teams have developed and tested methods to quantify AFO stiffness.[11-20] These methods are typically best suited for a research facility and involve a custom mechanical testing system. The testing rigs usually clamp the foot plate of the AFO to a rigid platform and move the proximal cuff[11-15] to quantify AFO stiffness around the anatomic ankle joint center[11,14,19] or the device axis of rotation.[15] Although testing devices have successfully estimated AFO stiffness, they generally fail to take into account the interaction between the device and biological limb. One device was built for use in a clinical space to test AFO stiffness while the patient is wearing their AFO.[16] However, the footplate is once again secured to a rigid platform, which is then rotated about the estimated anatomic ankle joint center to determine the overall limb stiffness while wearing the AFO.[16] This approach does not include the vertical load on the limb that likely influences device-limb interaction during gait. In this study we are testing a novel approach to measuring AFO-limb stiffness about the biologic ankle joint center to better represent the effects of AFOs on limb stiffness during gait.

A3) AFO-limb stiffness testing will use the same motion capture system used to collect gait biomechanics. The ability to collect reliable gait data across sites has been previously demonstrated[21,22] and the same techniques will be applied to this measurement. Muscle activity will be measured using non-invasive surface electromyography sensors on the skin. AFO-limb stiffness will be measured twice during the testing session in order to determine within-session reliability of the novel AFO-limb stiffness testing procedures.

Inclusion Exclusion Criteria:

Patient Inclusion Criteria

- Between the ages of 18 and 45
- Healthy without current complaint of lower extremity pain, spine pain, open wounds or active infections, or medical or neuromusculoskeletal disorders that have limited their participation in work or exercise in the last 6 months
- Able to hop without pain
- Able to perform a full squat without pain
- Ability to speak and understand English

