Each participant will be given time to accommodate to the brace prior to collection. Participants will then undergo testing in each study condition (Stiff, Compliant, NoBrace) to determine how orthosis stiffness affects gait biomechanics and overall joint stiffness. We will use well-established techniques to obtain a range of biomechanical data as individuals walk at self-selected and controlled speeds.

Personal/demographic and anthropometric information will be used to fully characterize the study participants. Demographic factors include characteristics that are independent of the health condition but can potentially influence physical performance and an individual's course of recovery. We will collect multiple variables that have been previously associated with outcomes, including race, ethnicity, and education to characterize the cohort. Anthropometric and demographic information, such as age, biological sex, height, weight, leg length, shoe type, shoe length and width will also be used to characterize the cohort.

Patient-reported outcomes questionnaires will be used to evaluate participant pain, comfort and smoothness. These patient-centric assessments will provide insight that can be used to interpret other study findings. We have used the selected measures in the target population and expect that they will effectively capture device-related outcomes.

Comfort and smoothness will be assessed using a modified version of the Socket Comfort Score, a reliable, valid, and sensitive measure of device fit and comfort.[23] These measures have been shown to effectively capture patient perception, are responsive to simple modifications to CDO device function, and will be applied in a manner consistent with a prior publication by the research team.[24] Comfort scores range from 0 = most

uncomfortable to 10 = most comfortable, and from 0 = least smooth to 10 = most smooth.[23]

Pain will be assessed using a standard 11-point numerical pain rating scale, in which 0 = no pain and 10 = worst pain imaginable, in a manner consistent with multiple other protocols.[25,26] Using this highly reliable approach, participants will be asked to rate their pain at the start of each session, and report their pain with movement in the device (if any) during each walking condition.

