Ground reaction force and motion capture data will be used to evaluate the motion and loading of the lower limb and CDO devices as participants walk on a level walkway at self-selected speed and a controlled speed based on leg length.[21,27] Ground reaction force and motion capture data will be used to evaluate the motion and loading of the lower limb as participants walk on an over ground walkway at self-selected speed and a controlled speed based on leg length.[21,27] A minimum of three non-collinear reflective markers placed on the skin to minimize skin-bone movement will be used to determine kinematics for the segments of interest (foot, shank, thigh, pelvis, trunk, arms and head). A pointer wand with a rubber tip will be used to identify bony landmarks for segment coordinate system definition. Visual 3D software (C- Motion Inc.) will be used to calculate segment and joint angles and velocities. Force plates imbedded in the floor will capture ground reaction forces. Data from successful trials will be analyzed using Visual-3D software package (C-motion Inc., Germantown, MD).[21] The ability to collect reliable data across sites has been previously demonstrated.[22] Techniques established by [name] will be used to assess ankle peak dorsiflexion, joint moments, and power.[21] The movement of the center of pressure (COP), the weighted average location of all ground reaction forces, has been directly related to prosthetic and orthotic device design, function, and participant preference.[24,28-30] The peak velocity of the COP and the time to peak will be determined as a percentage of stance, in a manner consistent with prior work by the research team.[24]

Muscle activity will be measured using non-invasive surface electromyography sensors on the skin. A total of 8 EMG electrodes will be placed on the participant, with 4 on each leg to measure activation of the soleus, tibialis anterior, and medial gastrocnemius and peroneus longus. EMG data will be collected bilaterally in the lower limbs and during normal walking and during in-vivo ankle stiffness testing. Participants will be given visual feedback to minimize the effects of muscle activity on measured joint stiffness. Participants will stand and sit with their foot (side with the Malleo-Lok AFO) on the force plate embedded in the floor and bring their knee forward over their stationary foot to deflect the device while minimizing muscle activity.

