Video recordings will be collected during walking trials. Recordings will include walking on the level over ground surface in each condition and at each walking speed. The camera will be positioned so the top of the field of view will be at the shoulders to minimize the likelihood of capturing the participants face, and the files will be stored securely as described in section X.4 and will only be available to members of the research team. Collection of video recordings is required during testing for quality control purposes. Video recordings will be removed from the video camera after being transferred to the secure network drive server and will be retained to facilitate future analysis consistent with "Data Storage for Future Use" section in the informed consent document.

Statistical Analysis Plan:

Analysis Methods:

There is one independent variable (IV) in this study, stiffness of the ankle brace (compliant and stiff). All the primary dependent variables (e.g. ankle moments, ankle range of motion, push-off power, ankle joint stiffness) will be evaluated using similar statistical approaches within each group. One-way repeated measure ANOVAs will be used to evaluate the effect of brace stiffness. Paired t-tests with Bonferroni-Holm correction will be used for post-hoc comparisons. Multiple trials will be collected for each condition during in-vivo ankle-CDO stiffness testing. Intraclass correlation coefficients and minimal detectable changes values will be calculated for in-vivo ankle-CDO stiffness between the average measurement for time point 1 and time point 2.

Power Analysis:

The number of participants proposed for this study are consistent with those from prior investigations by [name] related to AFO design. Thirteen participants was sufficient to detect differences associated with AFO stiffness in a recent study by [name] (PMID: 25193884). A total of 20 participants were included to adequately evaluate reliability in Aim 3.

Literature Cited:

21. Wilken, J.M., et al., Reliability and Minimal Detectable Change values for gait kinematics and kinetics in healthy adults. *Gait Posture*, 2012. 35(2): p. 301-7.
22. Kaufman, K., et al., Reliability of 3D gait data across multiple laboratories. *Gait Posture*, 2016. 49: p. 375-381.
23. Hanspal, R.S., K. Fisher, and R. Nieveen, Prosthetic socket fit comfort score. *Disabil Rehabil*, 2003. 25(22): p. 1278-80.

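### Does the SAP's silence on standing versus seated stiffness testing undermine the Aim 3 ICC and MDC, or the Aim 2 comparison?

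*Combined protocol and SAP*

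**What the plan says.** Two sections describe the stiffness test in the same words, Purpose and Procedures and Design and Methods: "Participants will stand and sit with their foot (side with the Malleo-Lok AFO) on the force plate embedded in the floor". The knee is then brought forward over the fixed foot while muscle activity is kept low. The test is done twice in the session.

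The third aim, under Objectives and Specific Aims, is: "Determine the within-session reliability of a novel in-vivo weight bearing approach to evaluating AFO" stiffness. Section A2 of Background and Significance says of an existing test on a worn device: "This approach does not include the vertical load on the limb that likely influences device-limb interaction during gait".

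Purpose and Procedures states that "lower limb stiffness and gait mechanics will be evaluated in healthy, able-bodied adult participants across three conditions", namely NoBrace, Compliant and Stiff. Posture is not one of the conditions.

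The SAP's Analysis Methods say: "Multiple trials will be collected for each condition during in-vivo ankle-CDO stiffness testing". The ICC and MDC are then "calculated for in-vivo ankle-CDO stiffness between the average measurement for time point 1 and time point 2". For the comparison between brace conditions, "All the primary dependent variables (e.g. ankle moments, ankle range of motion, push-off power, ankle joint stiffness) will be evaluated using similar statistical approaches", by one-way repeated-measures ANOVA with Holm-corrected paired t-tests. None of these sentences refers to posture.

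**The concern.** The procedure has two postures and the analysis text has none. One could take the single average per time point to include standing and seated trials alike. By the protocol's own argument about vertical load, the two postures need not measure the same stiffness if the seated foot carries less load, which is an assumption.

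Two things would then be at stake. For Aim 3, the ICC and MDC would belong to a two-posture mean, and someone who later ran only one posture would apply an MDC that does not fit it. For Aim 2, the ANOVA needs one stiffness value per participant and condition. Two postures at two time points offer 2 × 2 = 4 candidates, and no rule is written for choosing among them, so the choice could in principle follow the results.

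**Working it through.** **The plan's own figure.** Power Analysis gives 20 participants for the reliability aim. It states no expected ICC, interval width or power, so 20 cannot be rebuilt. The posture question does not touch it.

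**Reading the texts side by side.**

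1. The ICC sentence names two time points and an average. It names neither posture nor brace condition. Read strictly enough to merge postures, it would also merge Stiff, Compliant and NoBrace. That is implausible, because Purpose and Procedures wants to know whether the method separates those three. A reader who supplies a separate result per brace condition has no textual ground for refusing the same reading for posture.
2. Gait is collected at self-selected and controlled speeds, and Analysis Methods are equally silent on speed. That silence does not imply that speeds are averaged.
3. The criticism in section A2 is aimed at a test in which the footplate is fixed to a platform and rotated. In the new test the foot is on a force plate in both postures. The documents do not define weight bearing as standing only.

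**What merging would do, if it happened.** The documents give no variance, ICC or effect size, so every input below is assumed, with equal weight per posture.

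*MDC.* Let k be the seated-to-standing ratio of error SDs and r the correlation of errors. The two-posture MDC divided by the standing-only MDC is sqrt(1 + k² + 2rk) / 2.

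| k | r | Ratio |
|---|---|---|
| 1 | 0 | sqrt(2)/2 = 0.707 |
| 1 | 0.5 | sqrt(3)/2 = 0.866 |
| 0.5 | 0 | sqrt(1.25)/2 = 0.559 |
| 2 | 0 | sqrt(5)/2 = 1.118 |

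The first row is 1/sqrt(2), the gain from averaging two equally precise measurements. Doubling the number of standing trials would give the same ratio if trial errors are independent. It therefore shows the effect of averaging and is not evidence about posture. A two-posture MDC is also correct for a two-posture test; it misleads only someone who uses a different test.

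*ICC.* Let a and b be the standing and seated ICCs, with unit total variances, independent errors and correlation ρ between true values. The ICC of the mean is T/(T + E), where T = a + b + 2ρ·sqrt(ab) and E = (1 − a) + (1 − b).

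- a = 0.75, b = 0.95, ρ = 0.5: T = 1.70 + 0.844 = 2.544, E = 0.30, ICC = 0.895. At ρ = 0.9 it is 0.915.
- a = 0.90, b = 0.60, ρ = 0.5: T = 1.50 + 0.735 = 2.235, E = 0.50, ICC = 0.817. At ρ = 0.9 it is 0.850.

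The mean can look better or worse than the standing test, depending on values nobody has.

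*Aim 2.* If the Compliant–Stiff t-test has power p in each posture and the postures are independent, the two verdicts differ with probability 2p(1 − p): 0.32 at p = 0.80, 0.18 at 0.90, 0.095 at 0.95, 0.020 at 0.99. Positive correlation lowers this. Simulation with n = 20, an unadjusted 5% test and correlations from 0.7 to 0.3 gave 18% to 27% at 80% power, 11% to 16% at 90%, 6% to 9% at 95%, and under 2% at 99%. The documents give no effect size, so nothing favours 80%, and the SAP specifies Holm correction, which these figures leave out.

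**The case for a change.** The strongest case for a change is that it would be cheap. An MDC is valid only for the measurement it came from, the ICC and MDC are what Aim 3 delivers, and ankle joint stiffness is listed among the primary variables. One or two sentences would say whether averages are taken within posture and which posture and time point feed the ANOVA. If separate results are already intended, writing that down loses nothing.

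Part of this stands. The documents do not name the posture or time point for Aim 2, nor the posture for Aim 3, and a reader of the results should check which was used. What does not stand is the step from silence to a faulty analysis. No sentence directs that standing and seated trials be pooled, and the one-way ANOVA can be run for each posture without departing from the plan. The room for selective choice is also limited: the primary variables are an open list with no single confirmatory test, so showing both postures is the natural course.

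Adding a pass mark for excellent reliability would go beyond the posture gap. No cut-off appears in the documents. Requiring an ICC of at least 0.90 in all three conditions at n = 20, with every true single-measure ICC equal to 0.90 and conditions independent, would be met in about 12% of studies using the single-measure form and about 77% using the average-measure form.

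**Conclusion.** The observation is accurate: testing uses two postures and the SAP mentions neither. It is a missing definition that a competent analyst fills by averaging within posture, brace condition and time point and reporting standing and seated results separately. Following the plan as written produces no demonstrated wrong result.

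The possible sizes (an MDC 0.56 to 1.12 times the standing-only value, an ICC shifted either way, and verdicts differing in anything from under 2% to 27% of studies) all depend on assumed inputs. The MDC and ICC figures also depend on a pooling step the documents do not prescribe. The sample size of 20 is unaffected. No change to the plan is called for. This conclusion rests on the ordinary reading that levels left unmentioned, like brace condition and walking speed, are kept separate; it would fail only if the sponsor in fact pooled the postures.

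### Does naming Aim 3 as the reason for 20 participants, with no reliability target or calculation, call for a change to the plan?

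*Combined protocol and SAP*

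**What the plan says.** The Power Analysis paragraph of the Statistical Analysis Plan gives the sample size two supports. The first is precedent: "The number of participants proposed for this study are consistent with those from prior investigations by" the same investigators, and "Thirteen participants was sufficient to detect differences associated with AFO stiffness in a recent study". The second is specific to reliability: "A total of 20 participants were included to adequately evaluate reliability in Aim 3".

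Aim 3 concerns the repeatability of the in-vivo stiffness test, which the Purpose and Procedures section calls the study's secondary purpose. Hypothesis 3.1 reads: "We expect the novel approach to demonstrate excellent within-session reliability". Background item A3 sets two measurements: "AFO-limb stiffness will be measured twice during the testing session in order to determine within-session reliability". Under Analysis Methods, several trials are collected per condition and averaged at each time point, and "minimal detectable changes values will be calculated for in-vivo ankle-CDO stiffness between the average measurement for time point 1 and time point 2", alongside ICCs.

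The documents do not give an expected ICC, a numerical meaning for excellent, a lower limit, an interval width, an error rate or a power for Aim 3. They also do not mention confidence intervals for the ICC or MDC, or say whether these are computed per condition or pooled.

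**The concern.** The precedent of 13 is about detecting differences between stiffness levels and says nothing about reliability. Aim 3 is therefore the only specific reason for going to 20, and no figure stands behind it. The sample size cannot be reproduced, and it cannot be altered once the data are in.

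Two things seem to be at stake. An ICC from 20 people tested twice is imprecise, so a point estimate printed alone could be called excellent when the data also allow clearly lower values. The MDC, which a reader might use to judge whether a change in one person is real, would carry similar uncertainty unseen.

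**Working it through.** **Inputs from the documents.** n = 20 participants (Power Analysis); two measurements per person in one session (Background, A3); ICC and MDC between the two time-point averages (Analysis Methods). There is no figure of the plan's own to reproduce, because 20 is not derived from anything stated.

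**Assumptions.** Normal data, no systematic shift between the two tests, complete data, a consistency ICC, and ICC and MDC computed within one condition. The ICC values and cut-offs are not in the documents, so they are varied.

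**1. Interval for the ICC.** With two tests per person, F(r) = (1 + r)/(1 − r). The 95% limits are F(r) divided and multiplied by the 0.975 quantile of F(19, 19), which is 2.526, and converted back by r = (F − 1)/(F + 1).

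For r = 0.90, F = 1.90/0.10 = 19.
- Lower: 19/2.526 = 7.52, giving 6.52/8.52 = 0.765.
- Upper: 19 × 2.526 = 48.0, giving 47.0/49.0 = 0.959.

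| Observed ICC | 95% CI, n = 20 |
|---|---|
| 0.80 | 0.56 to 0.92 |
| 0.85 | 0.66 to 0.94 |
| 0.90 | 0.77 to 0.96 |
| 0.95 | 0.88 to 0.98 |

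The one-way and absolute-agreement forms give 0.769 to 0.959 at 0.90, so the choice of form hardly matters.

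**2. Interval for the MDC.** MDC95 = 1.96 × SD of the 20 within-person differences, on 19 degrees of freedom. The 95% limits are the estimate times √(df/χ²).
- 19 df: √(19/32.85) = 0.76 and √(19/8.91) = 1.46.
- 12 df (13 people): 0.72 and 1.65.
- 38 df (error pooled over two braces): 0.82 and 1.29.
- 57 df (pooled over three conditions): 0.85 and 1.22.

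The pooled figures need similar, independent errors across conditions.

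**3. Is 20 enough?** This needs a rule that the plan does not contain. Take as an illustration an 80% chance that the lower confidence limit reaches a cut-off c. That chance is P(F(n−1, n−1) ≥ q × F(c)/F(true)), where q is the F quantile for the limit used. The smallest n is:

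| True ICC, cut-off | Two-sided 95% limit | One-sided 95% limit |
|---|---|---|
| 0.95, 0.75 | 13 | 11 |
| 0.95, 0.80 | 17 | 14 |
| 0.90, 0.70 | 24 | 19 |
| 0.90, 0.75 | 34 | 27 |
| 0.90, 0.80 | 59 | 47 |
| 0.95, 0.90 | 63 | 50 |

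A precision rule divides in the same way. By the Bonett formula, a total interval width of 0.20 at ICC 0.90 needs 15 people, and a width of 0.15 needs 26. So 20 lies inside the range of answers, above some and below others. The observed ICC has to be about 0.89 for the two-sided lower limit to reach 0.75, and about 0.96 for it to reach 0.90.

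**The case for a change.** The strongest case for a change is that n is settled in advance, so an undefined claim of adequacy cannot be put right at analysis. The result could also mislead. If the true ICC is 0.85, an estimate of 0.90 or more still occurs with probability P(F(19, 19) ≥ 19/12.33) = 0.18. Under the two-sided rule above, true values of 0.85 and 0.90 have only a 22% and 56% chance of clearing 0.75. Stating a target, or stating what 20 delivers, would cost one paragraph.

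The arithmetic stands, and so does the observation that adequacy is not defined. Insufficiency does not follow. Every case in which 20 falls short uses a cut-off, a confidence rule and an 80% assurance brought from outside the documents. Hypothesis 3.1 is worded as an expectation and sets no bound to be tested. At the illustrative ICC of 0.90 the whole interval lies above 0.75, so doubt about the word excellent arises there only under a stricter cut-off. Averaging several trials at each time point reduces trial-level error, which makes the higher true ICCs more plausible, though the documents give no figure for this.

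The MDC range of −24% to +46% applies only to separate estimates by condition. Pooling narrows it at the same n, but it assumes similar error at deliberately different stiffness levels. That is a trade-off, and leaving pooling out is not an omission. The fear that no interval will be shown is drawn from a short plan's silence; the MDC factor depends only on the degrees of freedom, so a reader can recover it from n.

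**Conclusion.** The reason given for 20 participants is thin: adequacy for Aim 3 is undefined, but it is not shown to be unmet. At n = 20 with two tests, precision is 0.77 to 0.96 around an assumed ICC of 0.90, and 0.76 to 1.46 times a per-condition MDC. These figures rest on normal, complete data with no shift between tests; the ICC is an assumption, and the MDC factor does not depend on it.

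No change follows. The planned estimates are valid whatever the target would have been. Confidence intervals, the number of people with both tests, and a conclusion on Hypothesis 3.1 worded to match the interval are ordinary reporting that competent analysts supply. A larger sample would mean more visits of 3 to 4 hours for a secondary purpose, with no stated figure being missed.
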